2.5 Randomisation and Blinding

To ensure appropriate distribution of variables that may affect the primary endpoint, the primary randomisation was stratified by enrolling centre.

Neither patients nor site personnel (including the on-site AdreView™ scan reviewer) could be blinded to group assignment. Sites had to know whether patients were randomised to the AdreView™ or SoC groups in order to use the results of the scans in the AdreView™ group. However, the clinical investigator remained blinded to the values of H/M ratio obtained from the AdreView™ planar scan.

Both the DSMB and the CEAC reviewed patient data while blinded to enrolment group. The DSMB could have, should it have been regarded as necessary for their analysis, also reviewed patient data in an unblinded fashion.

3 STUDY ENDPOINTS

3.1 Efficacy Endpoints

3.1.1 Primary Endpoint

The primary endpoint is all-cause mortality.

3.1.2 Key Secondary Endpoints

- A composite of the rate of hospitalisation and death related to major complications of device implantation (i.e., need for thoracotomy, pericardiocentesis, or vascular surgery) and a composite of the rate of complications of long-term device therapy (i.e., infection not

leading to hospitalisation, lead and/or generator removal/replacement, inappropriate shocks, explantation). (AdreView Low-risk group vs. SoC H/M ≥ 1.6);

- Cardiac death (composed of SCD, death due to cardiac arrhythmia, death due to HF, and death due to other cardiovascular causes);
- The rate of hospitalisation for cardiovascular cause;
- The rate of all-cause hospitalisation;
- A composite of the occurrence of resuscitated life-threatening ventricular tachycardia, unstable ventricular tachyarrhythmias, SCD and resuscitated cardiac arrest.

3.1.3 Additional Secondary Endpoints

- The occurrence of syncope;
- The clinical and healthcare resource utilisation data including, ICD implantation, all hospitalisations, treatment of AEs, and AdreView™ administration;
- A composite of the rate of hospitalisation and death related to major complications of device implantation (i.e., need for thoracotomy, pericardiocentesis, or vascular surgery) and a composite of the rate of complications of long-term device therapy (i.e., infection not leading to hospitalisation, lead and/or generator removal/replacement, inappropriate shocks explantation). (AdreView™ group vs. SoC).

The above listed primary and secondary endpoints (except all-cause hospitalization and the clinical and healthcare resource utilization data) will be reviewed and validated by the CEAC for all patients.

3.2 Safety Endpoints

- Clinical laboratory parameters: serum biochemistry and haematology
- Vital signs: systolic/diastolic blood pressure, respiratory rate, heart rate, intermittent pulse oximetry
- 12-lead ECG
- Physical examination (complete and brief)
- Injection site monitoring before and after injection (with findings recorded pre-administration, 15 minutes post-administration, and at discharge from the imaging suite)

- Pre-randomisation events
- Post-randomisation events (AEs, serious AEs [SAEs], and AdreView™-emergent AEs)

4 ANALYSIS POPULATIONS

4.1 Definition for Analysis Populations

Unless otherwise specified, all the endpoints will be analysed by study arm (the AdreView™ group or the SoC group) which is the group at the time that patient was randomised.

4.1.1 Safety Analysis Set (Safety Population)

The safety analysis set comprises all patients who signed the informed consent form and met all of the inclusion criteria and none of the exclusion criteria.

4.1.2 Full Analysis Set (Efficacy Population)

The full analysis set is defined as patients in the safety analysis set who were randomised to the AdreView™ group or the SoC group.

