7.4 Withdrawal and Termination Criteria

7.4.1 Patient Withdrawal

There are no formal withdrawal criteria for this study. During the conduct of the study, the Sponsor may review the safety data for trends and signals that would indicate the need for withdrawal of a patient.

In accordance with the Declaration of Helsinki, each patient is free to withdraw from the study at any time. Investigator(s) also have the right to withdraw patients from the study in the event of illness, AEs, or other reasons concerning the health or well-being of the patient, or in the case of lack of co-operation.

Should a patient decide to withdraw after administration of AdreView™, or should the investigator(s) decide to withdraw the patient, all efforts will be made to complete and report the observations up to the time of withdrawal as thoroughly as possible. A complete final evaluation at the time of the patient's withdrawal should be made and an explanation given of why the patient is withdrawing or being withdrawn from the study. As this is an intention to treat analysis, all patients should be followed for the primary endpoint of all-cause mortality if at all possible. ICD crossover or having a secondary endpoint is not a reason to withdraw from the study.

The reason for withdrawal must be noted in the electronic Case Report Form (eCRF). If the reason for withdrawal is a serious adverse event (SAE), monitoring will continue until the outcome is evident. The specific event or test result(s) must be recorded in the eCRF. The reason for withdrawal must be noted in the eCRF. If the reason for withdrawal is a clinical AE, monitoring will continue until the outcome is evident. The specific event or test result(s) must be recorded in the eCRF. Patients withdrawing prior to completing the study may be replaced.

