9.6 End of Study Visit

This will be an event-driven study. Patients will be enrolled and followed up until sufficient endpoints have accrued (247 primary endpoint events). All patients will then attend an end-of-study visit within 1 month.

If a patient discontinues prematurely, he/she will attend an end of study visit at that time. As this is an intention-to-treat analysis, all patients should be followed for the primary endpoint of all-cause mortality if at all possible.

The following parameters will be collected:

- Medical history (with identification of study end-points)
- Concomitant medications
- Vital signs (blood pressure, heart rate, respiratory rate, and pulse oximetry)
- A brief physical examination will be performed.
- AEs, SAEs and AdreView™-emergent AEs
- All data related to primary and secondary endpoints
- ICD interrogation (for those patients with an ICD); may be performed remotely within ±5 days of follow-up visit.

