12.2 Populations for Analysis

A patient is defined as having been included into the study if he/she has met all inclusion criteria, none of the exclusion criteria, and has been assigned to 1 of the enrolment groups (the AdreView™ group or the SoC group). The primary efficacy population is defined as those patients who were randomised to the AdreView™ group or the SoC group.

All randomised patients will be analysed for efficacy in the group to which they were randomised.

The safety population is defined as all patients who were enrolled in the study. All patients will be analysed for safety in the enrolment group to which they were assigned.

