12.2.1 Determination of Safety and Efficacy Population

The rules for determination of the efficacy populations (primary and secondary) and the safety population are given in Section 12.2 above. Protocol violations will play no part in patient inclusion in the efficacy or safety populations.

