5.4 Efficacy Analysis

5.4.1 General Considerations

The analysis of the efficacy data will be based on the efficacy population.

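### The SAP's full analysis set adds an eligibility condition that the protocol's intention-to-treat population for the primary mortality test does not have, and gives no reason

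*SAP*

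**What the plan says.** **SAP.** Section 4.1.1 defines the safety set as "all patients who signed the informed consent form and met all of the inclusion criteria and none of the exclusion criteria". Section 4.1.2 builds the efficacy set from it: "The full analysis set is defined as patients in the safety analysis set who were randomised". Section 5.4.1 then says: "The analysis of the efficacy data will be based on the efficacy population". That covers the primary analysis in 5.4.2, a Cox model tested against a hazard ratio of 1.2 at one-sided 0.025.

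**Protocol.** Section 12.2 defines the primary efficacy population as the patients randomised to either group and adds: "All randomised patients will be analysed for efficacy in the group to which they were randomised". On safety it says: "The safety population is defined as all patients who were enrolled in the study". Section 12.2.1 says: "Protocol violations will play no part in patient inclusion in the efficacy or safety populations". Section 7.4.1 says: "As this is an intention to treat analysis, all patients should be followed for the primary endpoint of all-cause mortality", and 9.6 repeats the point.

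Two protocol sentences could be read the other way. Section 12.2 opens by tying a patient's inclusion in the study to meeting the eligibility criteria, and 12.12 includes all randomised patients unless otherwise specified. Neither redefines the efficacy population.

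**The concern.** Nesting the full analysis set inside an eligibility-restricted safety set turns an all-randomised population into an eligible-only one. Post-randomisation exclusion is safe only when it rests on facts fixed before randomisation and is applied without regard to arm. The SAP guarantees neither.

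Some criteria reach past randomisation by their own wording. Exclusion 10 concerns interfering medication in the 2 weeks before AdreView, and protocol 9.2 schedules the scan within 15 (+7) days after randomisation. Inclusion 2 requires, for women of childbearing potential, a negative pregnancy test before AdreView, and protocol 9.3 repeats that test on the scan day. Protocol 8.4 and SAP 2.5 confirm that sites and patients know the arm by then.

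The same clause reaches safety. Read literally, a randomised but ineligible patient leaves the by-arm safety summaries, though not necessarily the listings. The set also admits eligible, consented patients who were never randomised and so have no arm to be summarised in.

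The SAP gives its reason for replacing centre by country as stratum (section 5, small sites) and for dropping the testing hierarchy (5.4.4, early termination). It gives none for this change.

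**Working it through.** **1. Comparing the definitions**

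| Question | Protocol | SAP |
|---|---|---|
| Who is in the primary efficacy set? | All randomised (12.2) | Randomised and in the safety set (4.1.2) |
| Is eligibility a condition? | No; violations are irrelevant (12.2.1) | Yes, through 4.1.1 |
| Who is in the safety set? | All enrolled (12.2) | Consented and eligible (4.1.1) |
| Reason for the change | – | None given |

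A patient randomised in error is in the protocol's primary analysis and, as worded, not in the SAP's. The sets coincide only if *met* in SAP 4.1.1 means met as judged at enrolment, which the SAP does not say.

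**2. Reproducing the design figure**

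Inputs from protocol 12.8: assumed HR 0.84, margin 1.20, one-sided alpha 0.025, power 80%, 1:1 allocation.

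Events = 4(1.960 + 0.842)² / [ln(0.84/1.20)]² = 246.8, rounded up to **247**. This matches the plan.

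**3. Power if ineligible patients are dropped evenly**

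The documents give no count, so the shares are assumptions, with deaths lost in proportion.

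Power = Φ(ln(1.20/0.84) × √d / 2 − 1.96), with ln(1.20/0.84) = 0.3567.

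| Dropped | Deaths d | Power |
|---|---|---|
| 0% | 247 | 80.0% |
| 1% | 244.5 | 79.6% |
| 5% | 234.6 | 78.0% |

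**4. Bias if removal differs by arm**

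Assume exponential survival, a true HR of 1.00, and 36-month mortality of 12.34% in both full arms, the midpoint of the protocol's 11.34% and 13.33%. The full-arm hazard is −ln(1 − 0.1234)/36 = 0.003658 per month. An excess share e of the AdreView arm, with hazard r times that of the rest, is removed with its deaths and its follow-up. The hazard b of those who remain solves

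(1 − e)(1 − exp(−36b)) + e(1 − exp(−36rb)) = 0.1234,

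and the observed HR is b / 0.003658.

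| Excess e | r = 0.5 | r = 1 | r = 2 |
|---|---|---|---|
| 1% | 1.005 | 1.000 | 0.991 |
| 5% | 1.027 | 1.000 | 0.955 |

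Removing higher-risk patients from the AdreView arm favours non-inferiority. Removing lower-risk patients works against it. If the excess is in the SoC arm, the directions reverse.

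**5. How far exclusion 10 can reach past randomisation**

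Days of the 14-day look-back that fall after randomisation = min(scan day, 14). A day-5 scan gives 5 of 14, a day-10 scan gives 10 of 14, and scans on days 14 to 22 give all 14. This shows overlap in time, not bias.

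**The case against.** The best defence is that SAP 4.1.1 only means to remove screen failures. The schedules in both documents mark the eligibility check at screening/enrolment only. Protocol 9.1 requires every criterion to be satisfied and allows no prospective waivers, and under 9.2 the system allocates only patients allowed to continue. The SAP wording also resembles the opening sentence of protocol 12.2. On that reading few or no randomised patients would be lost.

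The post-randomisation route is also possible rather than documented. Protocol 8.5 leaves interfering medication to the investigator, who may withdraw the patient, and 7.4.1 still wants withdrawn patients followed for mortality. The stated consequence of a positive scan-day pregnancy test is that dosing does not start. Both arms are scanned in the same window, so no step in the plan by itself makes exclusion differ by arm. Finally, protocol 12.13 requires deviations from its statistical analysis to be explained in the study report.

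Much of this stands as a limit on size. It makes a large number of affected patients less likely, and differential removal is a risk rather than something shown. It does not cure the rule. A patient randomised in error still did not meet the criteria, and two criteria are anchored to a dose given after open-label randomisation. Reporting under 12.13 would not restore the analysis set, and the SAP does not identify this as a deviation.

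**Conclusion.** The concern holds. The SAP's population for the primary test contradicts explicit protocol text, and no reason is given. The effect is nil if no randomised patient failed a criterion, or if *met* is taken as judged at enrolment. Otherwise its size and direction are unknown.

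The illustrations rest wholly on assumed shares and hazards, and early termination means the 247 deaths may not be reached, so the power figures are context only. They suggest the power loss is minor and that bias is the larger issue: negligible at a 1% excess, up to about 4.5% on the hazard ratio scale at a 5% excess with doubled hazard. The case does not depend on those figures. It rests on the loss of the intention-to-treat comparison in an open-label non-inferiority trial, and it must be corrected before lock. The safety-set wording is a secondary point.

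**What to change.** Replace the two definitions:

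- **SAP 4.1.2:** *The full analysis set is all randomised patients, analysed in the arm to which they were randomised, regardless of eligibility or other protocol violations.*
- **SAP 4.1.1:** *The safety set is all enrolled patients (protocol 12.2), with no eligibility condition; never-randomised patients are listed separately from the by-arm summaries.*

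The SAP should also say what counts as enrolled, since the protocol uses the term loosely. An eligible-only set can be kept at most as a labelled sensitivity analysis.

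The cost is two sentences. No new data are needed, and SAP section 1 places sign-off before database lock, so the change fits there.

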5 ANALYSIS CONVENTIONS

Post-text tables and listings will be prepared in accordance with the ICH M2 Guidelines [\[ICH 2008\]](#). The information and explanatory notes to be provided in the “footer” or bottom of each table and listing will include the following information:

1. Date and time of output generation;
2. SAS® program name, including the path that generates the output;
3. Any other output-specific details that require further elaboration.

In general, tables will be formatted with columns displaying findings based on the study arm for all patients. The summary tables will clearly indicate the number of patients to which the data apply and unknown or not performed are distinguished from missing data.

Supportive individual Patient Data Listings, as a minimum, will be sorted and presented by the study arm, patient number, and visit date, if applicable.

This section details general conventions to be used for the statistical analyses. The following conventions will be applied to all data presentations and analyses.

- Summary statistics for categorical variables will consist of the number and percentage of responses in each level. The number and percentage of responses will be presented in the form XX (XX.X%).
- Summary statistics for continuous variables will consist of the sample size (n), mean, median, standard deviation (SD), first quartile, third quartile, minimum, and maximum values.
- All mean, median and quartile values will be formatted to one more decimal place than the measured value. SD values will be formatted to two more decimal places than the measured value. Minimum and maximum values will be presented with the same number of decimal places as the measured value.
- All p-values, if applicable, will be rounded to 4 decimal places. All p-values that round to 0.0000 will be presented as ' <0.0001 ' and p-values that round to 1.0000 will be presented as ' >0.9999 '. Two-sided P-values < 0.05 will be considered to be statistically significant unless otherwise specified.
- All summary tables will include the analysis population sample size (i.e., number of patients).
- Study Day 1 is defined as the date at which the patient was randomised. All study days are determined relative to Day 1.
- Study days prior to Day 1 will be calculated as:
 - Study Day = Assessment Date – Randomisation Date
- Study days after Day 1 will be calculated as:
 - Study Day = Assessment Date – Randomisation Date + 1.
- Baseline values will be defined as the last non-missing value recorded prior to randomisation.
- Change from baseline will be calculated as follows:
$$\text{Change} = \text{Post-baseline value} - \text{baseline value.}$$
- All pre- and post-enrolment assessments including unscheduled or repeat assessments will be included in the data listings.
- Date variables will be formatted as YYYY-MM-DD for presentation.

- Tables, figures, and listings will be presented in landscape orientation.
- SAS® Version 9.4 or higher will be the statistical software package used for all data analyses.

Definition of Analysis Windows

There are no visit windows for this study. For the statistical analyses, data will be analyzed by the nominal visit that was collected on the electronic case report form (eCRF).

Unscheduled visits will not be used in the by-visit analysis, but will be used for the following where appropriate: 1) derivations of baseline/last on-treatment measurements; 2) derivations of the maximum/minimum on-treatment values and maximum/minimum changes from baseline values for safety analyses; 3) data listings.

Definition of Missing Data Imputation

Missing values will not be substituted by estimated values, but treated as missing in the statistical evaluation.

Pooling of Enrolment Site

Due to the small number of patients that may have been enrolled at each study site, country will be included in the model as the stratification factor instead of the enrolment site. If there are countries that enroll only a small number of patients, the sponsor will review and provide the appropriate pooling strategy.

5.1 Demographics, Baseline Characteristics, Medical History, and Prior/Concomitant Medications

5.1.1 Demographic and Baseline Characteristics

Demographic information (age, height, weight, and body mass index [BMI]) will be summarized using descriptive statistics and p-values of the comparison between SoC and AdreView™ group will be presented by performing a two sample t-test. Gender and race will be summarized by counts and percentages and p-values of the comparison between the SoC and AdreView™ group will be presented by using a Chi-square test.

5.1.2 Medical and Surgical History

Medical and surgical history data will be summarized and presented using category and conditions/procedures as captured on the eCRF. The number and percentage of patients with a

particular condition/procedure will be summarized for each study arm. Patients reporting more than one condition/procedure within a category will be counted only once for that category.

5.1.3 Prior and Concomitant Medications

Any medications taken by the patient within 30 days before screening and up to the end of study visit will be summarized by counts and percentages using the World Health Organization Drug Dictionary (WHO-DD) March 2016 version, and grouped by primary and secondary classes, if applicable.

A prior medication is defined as any medication taken prior to the first AdreView™ administration. A concomitant medication is defined as any medication continued or newly taken after the first AdreView™ administration. If a medication cannot be classified as “prior” or “concomitant” because of missing/incomplete start and/or end dates, it will be classified as both prior and concomitant.

In addition, number of medications related to Guideline-Directed Optimal Medical Therapy (GDMT) at screening will be summarized and p-values of the comparison between the SoC and AdreView™ group will be presented by using a Chi-square test.

5.2 Patient Disposition

The number of patients for each of the following categories will be summarized.

- Patients screened/enrolled
- Patients included in the safety analysis set
- Patients included in the full analysis set
- Patients withdrawn from the study and the reason for withdrawal

5.3 Study Drug Exposure

For each AdreView™ administration, the dose (MBq) and volume (mL) will be summarized using descriptive statistics.

5.4 Efficacy Analysis

5.4.1 General Considerations

The analysis of the efficacy data will be based on the efficacy population.

5.4.2 Primary Efficacy Analysis

The primary endpoint is the hazard ratio of the all-cause mortality between the AdreView™ group and SoC. The primary efficacy endpoint will be analyzed for non-inferiority (NI) with the NI boundary equal to 1.2. If the upper bound of the confidence interval for the HR is less than 1, superiority will be claimed/ established.

The hypothesis testing for the primary objective is:

$$H_0: \text{hazard ratio (HR)} (\text{AdreView}^{\text{TM}} \text{ group} / \text{SoC}) \geq 1.2$$

$$H_a: \text{HR} (\text{AdreView}^{\text{TM}} \text{ group} / \text{SoC}) < 1.2$$

Cox proportional hazards model stratified by country, with study arm (AdreView™ group vs SoC) as the only covariate will be performed at a 1-sided alpha value of 0.025 for the primary endpoint.

Kaplan-Meier plot will be presented by method of treatment guidance. Patients who are still alive at the time of data base lock will be censored at the last known-alive date.

5.4.3 Secondary Efficacy Analyses

5.4.3.1 Key Secondary Endpoints Analyses

- A composite of the proportion of patients with hospitalisation or death related to major complications of device implantation (i.e., need for thoracotomy, pericardiocentesis, or vascular surgery) and a composite rate of complications of long-term device therapy (i.e., infection not leading to hospitalisation, lead and/or generator removal/replacement, inappropriate shocks, explantation). This endpoint will be analysed for superiority (odds ratio of AdreView™ vs SoC < 1.0). These proportions will be compared between the patients with H/M ≥ 1.60 in the AdreView™ group and the patients with H/M ≥ 1.60 in the SoC group, using the Cochran-Mantel-Haenszel (CMH) test stratified by country, using a 2-sided alpha value of 0.05.
- Cardiac death. The occurrence of this event will be analysed using a Cox proportional hazards model as described in the primary efficacy analysis (NI, using an NI margin of 1.20). Kaplan-Meier plot will be presented by method of treatment guidance. Patients who were alive or who had died from other than cardiovascular causes at the time of data base lock will be censored at the last known-alive date.
- Rate of hospitalisation for cardiovascular cause. The odds ratio of this rate will be compared between the AdreView™ and SoC groups using the CMH test stratified by country (NI, using an NI margin of 1.20).

- Rate of all-cause hospitalisation. The odds ratio of this rate will be compared between the AdreView™ and SoC groups using the CMH test stratified by country, (NI, using an NI margin of 1.20).
- A composite of the occurrence of resuscitated life-threatening ventricular tachycardia, unstable ventricular tachy-arrhythmias, SCD and resuscitated cardiac arrest. The first occurrence of these events will be analysed using a Cox proportional hazards model as described in the primary efficacy analysis (NI, using an NI margin of 1.20). Kaplan-Meier plot will be presented by the study arm. Patients who had not experienced any of the events at the time of data base lock will be censored at the last known-alive date.

